### **6.5.1 Extent of exposure**

Extent of exposure will be summarized for the SAF by treatment group, using descriptive statistics. Patients who switched from placebo to darolutamide during the open-label period will be described.

Duration of study treatment will be calculated in days and presented in months as the date of the last dose of any study treatment – date of the first dose of any study treatment + 1.

Dose modifications will be summarized.

### **6.5.2 Adverse events**

All adverse events (AE) whether considered drug-related or not, will be reported on the case report form (CRF) with diagnosis, start/stop dates, dates of any grade change, action taken, whether treatment was discontinued, any corrective measures taken, and outcome. For all events, the relationship to treatment and the severity of the event will be determined by the Investigator. AEs will be classified and coded using the National Cancer Institute (NCI) Common Terminology Criteria Adverse Event (CTCAE), version 4.03.

The treatment period for this study, for purposes of safety analyses, extends from the initiation of study treatment until 30 days after the last administration of study treatment.

Each change in AE grade was entered as a separate record with no automatic link to the original AE record, which may lead to variations of the verbatim for the same AE. This makes a correct grouping of AE grades, which actually belong together, not always possible. An AE is considered as treatment-emergent (TEAE) if there is an AE record which starts during treatment or within the post-treatment time window of 30 days.

For further definitions of the terms AE, SAE, seriousness, intensity, causal relationship with treatment, causal relationship to protocol-required procedures, action taken, and outcome; see Protocol Section 6.6.1.

Descriptive summary tables (frequency and percentage of patients, not of events) will be presented by treatment group and MedDRA version 24.0, or the most recent version for the following:

- Pre-treatment AEs
- TEAEs
- TEAEs with grade 3, 4, or 5
- TEAEs occurring in at least 1% of patients
- TEAEs occurring in at least 5% of patients
- TEAEs leading to study drug withdrawal
- TEAEs leading to dose reduction
- TEAEs leading to drug interruption
- TEAEs leading to dose reduction and/or drug interruption
- Drug-related TEAEs
- Drug-related TEAEs with grades 3, 4, or 5
- Drug-related TEAEs occurring in at least 5% of patients in any treatment group
- Drug-related TEAEs leading to study drug withdrawal
- Drug-related TEAEs leading to dose reduction
- Drug-related TEAEs leading to drug interruption
- Drug-related TEAEs leading to dose reduction and/or drug interruption
- Interval specific and cumulative event rates for TEAEs (for TEAEs with at least a 5% total incidence rate (any grade)).
- Post-treatment non-treatment-emergent AEs

Listings of non-treatment-emergent AEs and treatment-emergent AEs not coded per NCI-CTCAE dictionary will be created.

No subgroup analyses will be performed.

**Grouped AE terms defined as special topics**

Following TEAEs are considered as special topics, [Table 6–1](#):

**Table 6–1: MedDRA search criteria for special topics**

Grouped term	MedDRA search criteria
Bone fractures	HLT: Fractures and dislocations NEC (without PTs: Joint dislocation, Joint dislocation pathological) HLT: Limb fractures and dislocations (without PT: Radial head dislocation) HLT: Pelvic fractures and dislocations HLT: Skull fractures, facial bone fractures and dislocations HLT: Spinal fractures and dislocations (without PT: Dislocation of vertebra) HLT: Thoracic cage fractures and dislocations (without PT: Dislocation of sternum))
Fall	PT: Fall PT: Accident
Seizure	MLG: Seizures
Fatigue	MLG: Decreased general strength and energy PT: Lethargy; PT Chronic fatigue syndrome; PT Malaise
Weight decreased	MLG: Weight decreased

MLG: MedDRA Labeling Grouping; PT: Preferred Term; HLT: High Level Term

Following tables will be created for the TEAE of special topics as defined above

- TEAEs
- TEAEs leading to study drug withdrawal
- TEAEs leading to dose reduction
- TEAEs leading to drug interruption
- Exposure adjusted special topics TEAEs per 100 patient years
- Prevalence rates for most common TEAEs
- Risk ratio for TEAEs
- Treatment-emergent SAEs (TESAEs)

Fracture events will be described by a cumulative incidence plot of fracture. A summary of treatment-emergent fracture by bone sparing agent use (bone sparing agent will be selected in CM dataset using ATC codes M05B drugs affecting bone structure and mineralization, A11CC Vitamin D and analogues, A12A Calcium, A12CD Fluoride and H05BA Calcitonins) at study entry will be provided. Association with weight decrease will be presented by histogram of fracture events by patient weight change (the weight collected closest to the start of fracture will be considered and compared to baseline weight).

A listing will be generated for patients with fall treatment-emergent events with syncope and/or loss of consciousness (using the MLG Syncope).

Timing of occurrence of fracture events based on first dose of study drug will be presented. A detailed summary of patients with fall and fracture events will be presented, in addition, a graph will be created to display the time to fall and time to fracture.

An overview of patients at risk for developing an AE seizure will be tabulated by displaying medical history.

To adjust for unequal lengths of study treatment period among patients, and potentially between treatment groups, an additional summary based on event rate per 100 patient years will be performed for all TEAEs, special topics TEAEs and all TESAEs occurring during the double-blind treatment. The event rate per patient is calculated as the total number of events divided by the total treatment duration in years. The treatment duration in years will be calculated as treatment duration in days divided by 365.25.

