To adjust for unequal lengths of study treatment period among patients, and potentially between treatment groups, an additional summary based on event rate per 100 patient year will be performed for all AEs, special topics AEs and all SAEs occurring after the first dose

of study treatment. The event rate per patient is calculated as the total number of events divided by the total treatment duration in years.

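### The exposure-adjusted adverse event rate counts onsets up to 30 days after the last dose but divides by treatment time that stops at the last dose

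*SAP*

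**What the plan says.** Supplement 7, section 6.5.2, adds a rate per 100 patient-years to adjust for unequal treatment lengths between patients and possibly between arms. It covers all treatment-emergent adverse events (TEAEs), "special topics TEAEs and all TESAEs occurring during the double-blind treatment". The formula is "The event rate per patient is calculated as the total number of events divided by the total treatment duration in years", with days converted to years by dividing by 365.25.

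Three definitions in the same supplement determine what goes into it:

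- **TEAE (6.5.2).** An event is treatment-emergent "if there is an AE record which starts during treatment or within the post-treatment time window of 30 days".
- **Duration of study treatment (6.5.1).** This is "the date of the last dose of any study treatment – date of the first dose of any study treatment + 1". The 30 days are not part of it.
- **Treatment period for safety purposes (6.5.2).** This separate term "extends from the initiation of study treatment until 30 days after the last administration of study treatment".

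SAP v4.2, section 6.5.2, uses the same formula ("The event rate per patient is calculated as the total number of events", over total treatment duration in years). It applies it to AEs, special-topic AEs and SAEs after the first dose and states no end to that window. Its section 6.5.1 defines duration as Supplement 7 does.

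On data entry, both SAPs say: "Each change in AE grade was entered as a separate record with no automatic link to the original AE record". They add that grades belonging to one AE cannot always be grouped correctly. The main AE tables count patients. Supplement 7 also plans exposure-adjusted incidence rates and an incidence rate ratio with a 95% confidence interval, without giving a formula for them.

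**The concern.** A rate per patient-year is interpretable only if events are counted over the same time that is put in the denominator. Here a patient who stops treatment can contribute events for 30 more days but no further time, so the rate is too high.

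The excess depends on exposure. Thirty days is a larger share of a short treatment than of a long one, so the shorter-exposed arm is inflated more. The rate was added precisely because exposure may differ between arms. Treatment continues until confirmed metastasis and the plan assumes an MFS hazard ratio of 0.65, so placebo exposure is expected to be shorter. The mismatch would then move the rate ratio in favour of darolutamide.

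The rates matter most for the special topics (fracture, fall, seizure, fatigue, weight decrease). They also matter for the Supplement 7 display of fracture, weight decrease, cardiac events and fall, which sets darolutamide double-blind plus open-label beside placebo double-blind.

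**Working it through.** **No plan figure to reproduce.** The documents state no AE rate, mean exposure or share of patients stopping. Alpha, power and event numbers do not enter. All exposures below are assumptions.

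**Formula.** Let T be mean treatment days, f the share of patients who stop and have the full 30-day window, and r the event rate after the last dose relative to the rate on treatment. Then

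planned rate / matched rate = 1 + f × r × 30 / T, taking 30.44 days per month as in SAP v4.2, section 4.5.

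**Effect on one arm's rate.**

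| Mean exposure | f = 1, r = 1 | f = 0.35, r = 1 | f = 0.35, r = 0.5 |
|---|---|---|---|
| 6 months | 1.164 | 1.058 | 1.029 |
| 12 months | 1.082 | 1.029 | 1.014 |
| 18 months | 1.055 | 1.019 | 1.010 |
| 24 months | 1.041 | 1.014 | 1.007 |

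The 12-month entry with f = r = 1 is 1 + 30 / (12 × 30.44) = 1 + 30 / 365.28 = 1.082. In terms of the rate itself, suppose the true rate is 100 per 100 patient-years and a patient is treated for 365.25 days. Expected events over treatment plus 30 days are 395.25 / 365.25 = 1.082. The planned rate is then 108.2 per 100 patient-years; with the 30 days also in the denominator it is 100.0.

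**Effect on the darolutamide/placebo rate ratio.** This is the quotient of the two arms' inflation factors (r = 1).

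| Darolutamide | Placebo | Factor on the ratio |
|---|---|---|
| 12 months, all stopped | 12 months, all stopped | 1.0821 / 1.0821 = 1.000 |
| 18 months, all stopped | 12 months, all stopped | 1.0548 / 1.0821 = 0.975 |
| 18 months, 40% stopped | 12 months, 70% stopped | 1.0219 / 1.0575 = 0.966 |
| 24 months, all stopped | 9 months, all stopped | 1.0411 / 1.1095 = 0.938 |

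A simulation based on the plan's MFS assumptions, with mean treatment of 11.8 months (darolutamide) and 10.8 months (placebo) and a constant event hazard, gave inflation of 1.038 and 1.047. The ratio is then multiplied by 1.038 / 1.047 = 0.991. In the formula above these factors correspond to f = 0.038 / 0.0835 = 0.455 and f = 0.047 / 0.0913 = 0.515. The discontinuation model behind the simulation is not documented, so it is indicative only.

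**Grade changes.** If every record were counted, the rate would be multiplied by the mean number of records per AE. The documents do not give that number and do not say that records are counted, so no size can be derived.

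**The case against.** **Other readings of the window.** The numerator phrase about events occurring during double-blind treatment could be taken to exclude post-treatment onsets. Alternatively, the safety treatment period, which does run to 30 days after the last dose, could be meant as the denominator. Either reading removes the mismatch. Neither is the natural one. The first phrase more plausibly separates double-blind from open-label, as section 6.5 of Supplement 7 does. The formula uses treatment duration, which 6.5.1 defines, and not treatment period. Even if one was intended, the text should say so.

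**The v4.2 numerator is bounded in practice.** This is largely right. Protocol 6.6.1.2 collects all AEs only until the end-of-study treatment visit, scheduled 28 (+7) days after the last dose. After that, only AEs related to study treatment or procedures are reported, but until the end of the study, so the numerator remains open for those.

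**The effect is small and the analysis descriptive.** Both are true. There are no formal safety tests, and the event rate is an additional summary.

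**Stronger inferences that the documents do not support.** A reader might infer that each grade change counts as a new event, so that one AE moving through grades 1, 2 and 1 counts three times. The SAPs keep record and AE apart, and saying that grouping is not always possible implies that it is attempted. A reader might also infer that the rate-ratio confidence intervals are too narrow because of repeated records. Supplement 7 names the incidence rate separately and shows it beside incidence proportions, which count patients; the protocol (7.8.1) likewise counts a patient once for incidence. The ratio may already be patient-based. A collapsing rule may also exist in documents not supplied, such as Supplemental SAP 4 or the operational manual cited in SAP v4.2, section 4.3. What remains is that the supplied text defines neither the event nor the unit of the incidence rate.

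**Conclusion.** The window mismatch follows from the SAPs' own definitions read literally. It inflates the event rates modestly: about 4% to 8% at mean exposures of 24 down to 12 months if all patients stop and the event rate is unchanged afterwards, and less if fewer stop or the rate falls. It shifts the darolutamide/placebo ratio by under 1% with near-equal exposure and by about 6% at 24 versus 9 months. With equal exposure and equal discontinuation the ratio is undistorted.

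The direction is firm under the literal reading, as long as some AEs start in the 30 days after the last dose. The size rests on the assumed T, f and r. The undefined event is a secondary point that needs clarification, not a demonstrated over-count. No test or alpha is affected.

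**What to change.** In section 6.5.2 of both SAPs, use the same window in numerator and denominator, in one of two ways:

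- Keep the TEAE definition and end each patient's time at the earliest of last dose + 30 days, death, data cut-off and, for double-blind rates, the first open-label dose.
- Keep treatment duration as the denominator and count only events with onset on treatment.

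The first keeps the rate aligned with the other TEAE tables. In v4.2, also state where the numerator window ends.

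Two sentences of clarification should be added:

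- Consecutive grade-change records of one AE count as one event. The rule must not merge separately reported events, such as two falls on consecutive days, so matching on preferred term and adjacent dates alone is not enough.
- State whether the incidence rate and its ratio count patients with a first event over time at risk to that event.

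The cost is SAP wording and a small programming change. No new data are needed, and the reported rates would generally be slightly lower.

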### **Additional AE groupings**

The following additional tables for treatment-emergent adverse events (TEAEs) will be created. In all tables, results will be shown by treatment group. The double-blind part of the study will be considered only for risk difference, risk ratio, interval-specific incidence and prevalence.

To increase the sensitivity of the analysis, the synonymous or pathophysiologically related TEAEs were grouped using following approaches:

- Utilization of MedDRA hierarchy – i.e. using grouping on the level of system organ class (SOC) or high level group term (HLGT) or high level term (HLT),
- Utilization of predefined customized MedDRA queries denoted as MedDRA Labeling Groupings (MLG). These MLG are created and centrally maintained by Bayer internal coding experts,
- Data driven approach was used for grouping of TEAEs, for which the mentioned above predefined grouping were not available/suitable. For this purpose, a customized MedDRA query was created by selection of MedDRA terms after the review of safety data, as shown in [Table 6–2](#).

Incidence proportions will be calculated as number of patients experiencing an event per number of patients exposed. Incidence proportions will be presented by worst CTCAE grade (grade 1 to grade 5, missing grade, any grade)

- by MedDRA SOC, HLGT, HLT, preferred term (PT) and worst CTCAE grade,
- by MLG, PT and worst CTCAE grade,
- by data driven grouping, PT and worst CTCAE grade.

A separate table will be created for PTs not covered by MLG or data driven grouping. A definition table for the groupings will be provided, showing the AE grouping, the type of grouping entity used for definition (e.g. MLG, combination of MLGs, MLG + PT, data

driven), the corresponding preferred terms, and the reported terms. Preferred terms which occurred in the data are marked with preceding asterisk (\*\*\*)).

The risk difference ‘Darolutamide – Placebo’ and risk ratio ‘Darolutamide/Placebo’ will be calculated together with 95% confidence intervals (CIs). No zero-cell correction will be applied for calculation of the risk ratio, i.e. in case of no events in the placebo arm the risk ratio will not be calculated. The incidence rate ratio for Darolutamide/Placebo will also be calculated with 95% CI.

Risk difference, risk ratio, incidence rate ratio with 95% CIs will also be calculated for the predefined grouped terms defined as special topics, see [Table 6–1](#).

Interval specific and cumulative incidence proportions will be created for grouped TEAEs (i.e. HLT/HLT, MLG, data driven grouping) with a 5% incidence proportion of at least 5% in either treatment group. The prevalence of these events will also be displayed for the same intervals. Prevalence will be calculated as the number patients with the respective TEAE starting or ongoing in the specific time interval, divided by the number of patients still being in the study at the beginning of the time interval.

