3. OVERALL STUDY DESIGN AND PLAN

This is a randomised, phase III, multicentre, double-blind, placebo-controlled efficacy and safety study of oral darolutamide (600 mg bid) in patients with nmCRPC who are at high risk for developing metastatic disease.

Approximately 1500 patients will be randomised to receive darolutamide or placebo in a 2:1 ratio in a double-blind manner. Randomisation will be stratified by PSADT (≤ 6 months vs. > 6 months) and use of osteoclast-targeted therapy (yes vs. no).

Randomised patients will receive study treatment until confirmed metastasis or intolerable AE.

The study has a design of 2 parallel groups. For each patient, the study may involve 1 to 2 variable length periods: a study treatment period (a double-blind part for darolutamide or placebo arms and an open-label darolutamide treatment phase) and a follow-up period.

The length of the periods for each patient will depend on the absence or presence of metastasis – after confirmed metastasis, the patient must be withdrawn from study treatment.

During the double-blind part, patients may be on study treatment (darolutamide or placebo arm) or at follow-up. After the double-blind part, patients who are on study treatment may continue open-label darolutamide treatment under the conditions outlined in Section 5.9.

Assessments will depend on the period the patient is in (see Table 3 and Table 4 for more details) and as described below.

The double-blind treatment (darolutamide or placebo arm) is planned to be continued until the total number of events for the MFS analysis have been reached (planned at approximately 385 events). During this part the treatment code will remain blinded.

Patients in the darolutamide arm at the time of unblinding may continue open-label darolutamide treatment according to Section 5.9 and will visit the study centre as outlined in Table 3 until the end of the study.

Patients in the placebo arm at the time of unblinding may cross over to open-label darolutamide treatment according to Section 5.9, or will receive subsequent treatment at the discretion of the investigator, and will visit the study centre as outlined in Table 4 until the end of the study.

After confirmed metastasis in the double-blind treatment phase or after metastasis is identified by local reading in the open-label treatment phase, the patient will be withdrawn from study treatment and will be followed as outlined in Table 4 until the end of the study.

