- ⁸ CT/MRI and bone scans are acceptable if performed within 42 days prior to start of study treatment. A local qualified site physician (e.g. site radiologist or PI, at the PI's discretion) must first review the screening scans and confirm the patient is non-metastatic before submitting the scans to central review to confirm eligibility. If the local qualified site physician detects metastasis, the scans should not be submitted to central review. For guidance on CT/MRI and bone scans performed at Week 16 and subsequent visits during double-blind treatment, see Section 6.1.2.4. Scans are acceptable if performed within 42 days prior to the start of open-label treatment visit. Imaging will be conducted every 16 weeks (± 7 days) during the open-label darolutamide treatment after the start of open-label treatment visit (see Section 6.1.2.5). Patients continuing open-label darolutamide will only have local imaging, central confirmation is not required.
- ⁹ New lesion(s) in bone scan must be confirmed by CT/MRI (whichever imaging was conducted at screening for soft tissue) or x-ray. If confirmatory scan is negative (does not confirm progression), the patient will continue study treatment and visit study centre as specified in the study event table.
- ¹⁰ All AEs including SAEs will be recorded from the date of signing IC and continuing until the end-of-study treatment visit (including open-label darolutamide treatment phase). Any AEs or SAEs that occur after the end-of-study treatment visit and which are considered to be related to the study treatment or any study procedures have to be reported and entered into

- the eCRF. When the eCRF is not available anymore, all SAEs considered study treatment related should be reported to Bayer using a paper SAE form. AEs related to study procedures and all SAEs will be recorded for screening failures.
- ¹¹ Once the patient has been withdrawn from study treatment, concomitant treatments will be recorded if used to treat new related or unresolved related AEs or if it is an antineoplastic therapy.
 - ¹² An optional PG IC for pharmacogenetic research study will be obtained at screening visit (or later during the study if feasible) unless precluded by local guidelines, e.g. IEC/IRB or regulatory authorities.

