6.1.3 Follow-up period

Patients with MFS events (double-blind treatment phase) or metastasis by local reading (open-label treatment phase) will enter the follow-up period and will be contacted every 16 weeks until death or the end of the study. Follow-up contact will be performed by visit or telephone. The following data will be captured during the follow-up contacts:

- BPI-SF and PCS subscale of FACT-P questionnaires. If the patient is contacted through physician visit, a paper questionnaire will be completed by the patient prior to meeting with the physician in the office. If the patient is contacted by phone, the caller will read each item from the questionnaires to the patient and record the responses on a paper questionnaire.
- ECOG performance status
- Any AEs or SAEs that occur after the end-of-study treatment visit and which are considered to be related to the study treatment or any study procedures have to be reported and entered into the CRF.
- Collection of concomitant treatments used to treat new related or unresolved related AEs, if applicable)
- Status of survival
- Date of first SSE
- Date of first prostate cancer-related invasive procedure
- Use of systemic antineoplastic therapies
- Collection of pain diary and dispensing a new pain diary, and collection of pain medications. If the patient is contacted by phone, the pain diary will be mailed back to the clinic. No pain diary will be dispensed when a patient is transitioning to the roll-over study.

In case the patient discontinues study treatment before confirmed metastasis in the double-blind treatment phase or metastasis by local reading in the open-label treatment phase without initiating any prohibited treatment, these patients will be followed as outlined in [Table 4](#) until the end of the study.

The follow-up period will end at each site when all patients at the site who are ongoing on treatment have transitioned into the roll-over study or discontinued from the study for another reason (e.g., consent withdrawn - with no further data collection, lost to follow-up). Patients who are in follow-up at the site will end follow-up.

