6.6.1.2 Assessment of adverse events

All AEs must be elicited, documented and reported by the investigator to the sponsor from the time that a study subject signs the IC form until the end-of-study treatment visit. See Section 4.6 for guidance on adverse event reporting for screening failures.

Any AEs or SAEs that occur after the end-of-study treatment visit and which are considered to be related to the study treatment or any study procedures have to be reported until the end-of-study. Additionally, SAEs considered study treatment related even beyond study end should also be reported.

SAEs and other significant AEs should be followed-up until resolved or until the event is considered chronic and/or stable outcome.

AEs may be notified to the investigator by the study subject, observed by the investigator clinically, or be an adverse change in laboratory assessment results. The investigator will

evaluate the subject's AEs by asking a standard question, such as "Since you were last asked, have you felt unwell or different from usual in any way?"

The investigator will assess and record the causality and severity of the AEs. Causality should be assessed in relation to the investigational product (see criteria for causality and severity below).

Causality criteria:

Related: The temporal relationship of the AE onset to the administration of the investigational product makes a causal relationship possible, and other drugs, therapeutic interventions or underlying conditions do not provide a sufficient explanation for the AE.

Not related: The temporal relationship of the AE onset to the administration of the investigational product makes a causal relationship unlikely, or other drugs, therapeutic interventions or underlying conditions provide a sufficient explanation for the AE.

Severity criteria:

All AEs will be graded with National Cancer Institute Common Terminology Criteria for Adverse Events (NCI CTCAE) version 4.03:
http://evs.nci.nih.gov/ftp1/CTCAE/CTCAE_4.03_2010-06-14_QuickReference_8.5x11.pdf.

The severity of the adverse event and the CTCAE term should be recorded in the appropriate section of the AE CRF. Severity is included in this grading and there is no separate severity assessment.

In case a patient experiences an AE that is not presented in NCI CTCAE, the severity will be assessed according to following criteria:

Grade 1 = Mild AE, transient in nature and generally not interfering with normal activities

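### TEAE prevalence is divided by everyone still in the study, including off-treatment patients who can no longer have a new TEAE; as written this understates prevalence, and more so on placebo if placebo patients stop earlier

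*SAP*

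**What the plan says.** SAP Supplement 7, Section 6.5.2, Additional AE groupings, builds prevalence from two parts.

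- Numerator: the "number patients with the respective TEAE starting or ongoing in the specific time interval".
- Denominator: that count is "divided by the number of patients still being in the study at the beginning of the time interval".

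The same section treats an event as treatment-emergent if a record "starts during treatment or within the post-treatment time window of 30 days". Protocol Section 6.6.1.2 requires all AEs to be collected "from the time that a study subject signs the IC form until the end-of-study treatment visit". That visit falls 28 to 35 days after the last dose (Table 3), and afterwards only events related to treatment or study procedures are reported.

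Leaving treatment is not leaving the study. Protocol Section 3 states that "after confirmed metastasis, the patient must be withdrawn from study treatment". Under Section 6.1.3 such patients "will enter the follow-up period and will be contacted every 16 weeks until death or the end of the study". Section 3 keeps patients who start a prohibited therapy in the study for survival status only.

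Supplement 7, Section 6.5, limits prevalence to the double-blind period. Protocol Section 3 describes the double-blind part as containing patients on treatment and patients at follow-up.

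**The concern.** The two halves of the fraction cover different people. A patient more than 30 days past the last dose cannot have a new TEAE but still counts in the denominator. Prevalence is therefore pulled down as off-treatment patients accumulate, and later intervals suffer most.

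The dilution need not be equal between arms. Withdrawal at confirmed metastasis is mandatory, and the trial is designed on the expectation that metastasis comes earlier on placebo. A drug with no effect on an event could then appear to carry a growing relative burden of it. Absolute prevalence would also be too low in both arms, which could hide a real late burden. The tables concerned show common grouped TEAEs over time by arm; prevalence is also listed for the special topics (fracture, fall, seizure, fatigue, weight decrease).

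**Working it through.** **The plan's own figure.** The documents give no prevalence figure. The inputs that drive time on treatment come from the sample-size sections (Protocol 7.1, SAP 3.1), whose stated power is 91%. Freedman's formula for 2:1 allocation is Φ(√(D·k)·(1−HR)/(1+k·HR) − 1.96). With D = 385, k = 2 and the diluted HR of 0.71, this is √770 × 0.29/2.42 − 1.96 = 1.365, so power is 91.4%. Schoenfeld's formula gives 88.6%; the plan used simulation. The inputs hang together.

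**Inputs for prevalence.**
- Placebo median MFS 25 months: λP = ln 2/25 = 0.0277 per month.
- HR 0.65: λD = 0.0180 per month, a median of 38.5 months.
- AE collection runs 30 days (0.99 month) past the end of treatment.
- Assumptions: exponential times, treatment stopping at the MFS hazard, patients staying in the study until death, and a common death hazard μ. Two cases are shown: no deaths, and median OS of 44 months in both arms (the placebo figure from a denosumab phase III study in Protocol 1.1).

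**Dilution if off-treatment patients add nothing to the numerator.** The share of in-study patients still under collection at month t is exp(−(λ−μ)(t−0.99)). The spurious darolutamide/placebo ratio is exp((λP−λD)(t−0.99)); μ cancels. At month 24 this is exp(0.0097 × 23.01) = 1.25.

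| Month | Share, no deaths (placebo / darolutamide) | Share, OS median 44 months | Ratio |
|---|---|---|---|
| 12 | 74% / 82% | 88% / 98% | 1.11 |
| 24 | 53% / 66% | 76% / 95% | 1.25 |
| 36 | 38% / 53% | 66% / 92% | 1.40 |

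A true on-treatment prevalence of 20% in both arms would appear at month 24 as 10.6% v 13.2% with no deaths, or 15.2% v 19.0% with median OS of 44 months. With HR 0.71 the ratios are 1.09, 1.20 and 1.33. With HR 1.0 they vanish.

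**Allowing ongoing events to stay in the numerator.** The definition counts ongoing events, so an event that outlasts treatment may still be counted. This was simulated with 200,000 patients per arm, the same AE process in both arms, an assumed median OS of 60 months and assumed 16-week intervals (the documents do not give the interval length for these tables). Month 24:

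| Mean AE duration | In-study denominator (placebo / darolutamide) | Ratio | Under-collection denominator |
|---|---|---|---|
| 1 month | 26.7% / 34.0% | 1.27 | 38.6% / 39.4% |
| 6 months | 11.4% / 13.8% | 1.21 | 15.6% / 15.6% |
| 24 months | 6.4% / 7.4% | 1.15 | 8.1% / 8.1% |

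Adding 20% discontinuation for other reasons by month 24, equally in both arms, gives ratios of 1.27, 1.21 and 1.12. Keeping ongoing events shrinks the distortion for long-lasting events but does not reverse it. With the under-collection denominator the arms agree to within about 2%.

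**The case against.** The best defence is that the intended analysis is already the right one. Supplement 7 titles its prevalence-over-time tables as covering the double-blind treatment period, and Section 6.5.2 defines the treatment period for safety as running to 30 days after the last dose. Together these point to an on-treatment-plus-30-days risk set, and if the programming follows them the problem disappears. This stands as evidence of intent. It does not override the only written definition of the denominator, which names patients still in the study.

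Several limits on the size and consequences also stand.

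- No discontinuation data are given. The 40% dropout rate in the sample-size section is not said to be from treatment or from the study, and unequal withdrawal for other reasons could move the between-arm difference either way.
- The ratio is free of the death hazard only if that hazard is equal in both arms.
- The month-36 ratio is given without knowing how many patients reach that interval in an event-driven trial.
- Supplement 7 is descriptive, has no formal safety tests and specifies no between-arm prevalence ratio. Event rates per 100 patient-years and exposure-adjusted incidence rate ratios with confidence intervals are planned alongside.

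Three stronger readings are tempting but unsupported. A reader might infer that interval-specific incidence has the same fault. The in-study denominator is written for prevalence only, and the overall incidence proportions use patients exposed, so no defect is shown there. A reader might infer that all events ongoing at the end of treatment go untracked. Protocol Section 6.6.1.2 requires SAEs and other significant AEs to be followed until resolved, chronic or stable. A reader might also infer that the formula flatters darolutamide. On the design's assumptions the relative distortion runs against it.

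**Conclusion.** The mismatch is in the text: the written denominator includes patients who can no longer enter the numerator with a new event. That understates prevalence in both arms. The larger understatement on placebo is an inference from the design's assumption of earlier metastasis there and from mandatory withdrawal; it is not an observed fact.

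Under those assumptions and equal death hazards, the spurious month-24 ratio is about 1.25 if off-treatment patients add nothing to the numerator, and about 1.1 to 1.2 if long-lasting ongoing TEAEs are kept. The 1.25 is near the top of the plausible range and should not be read as the expected distortion for every event. Nor do the documents establish that the reported comparison will be biased, since the table titles suggest a different risk set. No efficacy result, error rate or formal safety conclusion is affected. The point is worth correcting because the tables are meant to be read over time and by arm, and the correction is small.

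**What to change.** In Supplement 7, Section 6.5.2, define the prevalence denominator as patients who, at the start of the interval, are on double-blind treatment or within 30 days of their last double-blind dose. Restrict the numerator to the same patients, and state how a TEAE still ongoing after that window is handled. This aligns the definition with the table titles and with the section's own treatment period.

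The cost is a sentence of SAP wording and one changed denominator in the programs; no new data are needed. If the programs already use this risk set, the sentence alone is enough. The corrected risk set is still selected after randomisation, so the tables remain descriptive.
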